Use of Repetitive Transcranial Magnetic Stimulation to Augment Hypnotic Analgesia

Statistical Analysis Plan

NCT02969707

January 4, 2024

Data were collected and organized using the REDCap methodology, and analysis was performed in the SPSS v.26.0 environment. According to our preregistered plan, analyses were completed within the intention-to-treat principle, and reported P values are nominal. To test the change in HIP scores following SHIFT, pre- to post-SHIFT changes in HIP scores (Δ HIP) were calculated by subtracting the immediate post-spaced SHIFT score from the pre-spaced SHIFT score. Neither the pre- or post-spaced SHIFT HIP variables nor the Δ HIP scores met the criteria for the assumption of normality (all Shapiro-Wilk P values < 0.001), rendering the first step in our preregistered plan of testing our hypotheses using analysis of variance (ANOVA) inappropriate. As such, we used non-parametric tests; within-group pre/post-SHIFT changes in HIP scores were tested using a two-tailed Wilcoxon signed-rank test. Two-tailed Mann-Whitney U-tests were used for group comparisons of Δ HIP scores between the active and sham groups. Effect sizes for the non-parametric tests were calculated using Cohen's r statistic. The study blind was tested using the chi-squared test.

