Continuous TBS Session: The continuous TBS will be applied using the Cool-B65 A/P coil which has a built in sham system. The Cool-B65 A/P coil is capable of delivering either active or sham rTMS in a manner that is randomized by the system itself and therefore blinded to the treater. The sham setting on this coil looks and sounds similar to the active setting, but has a hidden aluminum plate blocking actual stimulation. The Magventure device holds a blinded key code that is kept by the unblinded CRC. The operator is instructed to flip the coil to correspond with the key code, but does not know the stimulation group (active versus sham).

Stimulation Dose: This study utilizes two applications of 800 pulses of continuous TBS at 80% of the resting motor threshold as this has been demonstrated effective in producing a prolonged change in cortical excitability (30) as well as being demonstrated as safe(17). We will adjust the dose based off of the difference between motor cortex to skull and prefrontal cortex to skull measurements as has been previously reported(92). The spaced application of theta-burst stimulation (TBS) approach was chosen because this study will require more than an hour of modulation of the target in order to complete the scan sessions. The spaced approach has been demonstrated to have a much longer duration of effect than a single 800-pulse cTBS stimulation session(27, 28, 30, 79). The fifteen minute spacing between the two 800-pulse cTBS applications is essential because it has been demonstrated that prolonged stimulation approaches without spacing in between can cause a reversal of intended effect(80).

Stimulation Site: The spaced cTBS approach utilized for this study will be applied to the left dorsolateral prefrontal cortex (L-DLPFC) in the sub-region that has the highest functional connectivity with the dorsal anterior cingulate (dACC). This will be done through the use of neuronavigation hardware coupled with the latest in cutting edge targeting(81). This study will

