- Spectroscopy: Non-invasive magnetic resonance spectroscopy (MRS) will be used to quantitatively measure brain metabolites, including both inhibitory and excitatory neurotransmitters as well as markers of inflammation.

Pre-rTMS Stroop Assessment

Hypnotic Stroop and Non-Hypnotic Stroop Pre-rTMS Scan Session: This session includes all of the pre-rTMS questionnaires, behavioral evaluations and scans necessary to compare to the post-rTMS.

- Medication Washout, Drug Screen, Pregnancy Test Form: This form will be administered at the beginning of each pre-rTMS assessment to ensure medication washout compliancy (if applicable), document drug screen results, and screen for pregnancy (if applicable).
- Hypnotic Induction Profile: This administration of the HIP will serve as the baseline measure for comparison after the rTMS stimulation session(87). HIP will be measured on three separate occasions throughout the stroop assessment visit - 1) immediately following the pre-rTMS stroop MRI session, 2) immediately following rTMS, and, 3) immediately following the post-rTMS stroop MRI session.
- Stroop Task: This administration of the Stroop task will serve as the baseline measure for comparison to the post-rTMS session(32, 118).
- Pre-TMS Hypnotizability Scan Session (1 hour duration)
 - Structural Acquisition (T1): This structural scan is necessary for several reasons: demonstration that the participant's brain is structurally normal, imaging analysis, and rTMS targeting(81).
 - BOLD fMRI Acquisitions
 - Resting State: This is the baseline scan required for the primary endpoint. Individuals with high hypnotizability have been demonstrated to have higher functional connectivity between the dorsolateral prefrontal cortex and the dorsal anterior cingulate cortex (31).
 - Stroop Task: Brain activity while performing conflict tasks has been demonstrated to be different depending on a subject's level of hypnotizability. This baseline would demonstrate the subject's normal functional brain response to the Stroop Task

(32). Functional brain response to the stroop task will be measured following hypnosis (Hypnotic Stroop) and non-hypnosis (Non-Hypnotic Stroop) audio instructions. These acquisitions will be randomized to prevent order effects. Highly hypnotizable individuals can have a loss of the Stroop Effect with specific post-hypnotic instruction (119, 120) which correlates with the reduction in neural activity during conflict (35).

Pre-rTMS Analgesia Assessment

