Pre-rTMS Analgesia Session: This hour-long scan session includes all of the pre-rTMS questionnaires, behavioral evaluations, and scans necessary to compare to the post-rTMS.

- Medication Washout, Drug Screen, Pregnancy Test Form: This form will be administered at the beginning of each pre-rTMS assessment to ensure medication washout compliancy (if applicable), document drug screen results, and screen for pregnancy (if applicable).
- Pain Thresholds: Baseline heat-pain thresholds and supra-pain thresholds will be determined for each volunteer based on responses to computer-controlled thermal stimuli delivered to the left forearm with a 30 x 30 mm advanced thermal stimulator (ATS) thermode (Medoc Pathway Model ATS). Thresholds will be measured using a standard method of limits protocol. Specifically, thermal pain threshold and tolerance values will be assessed outside the MRI scanner to identify a moderate pain intensity value that will be applied during the hypnotic and non-hypnotic analgesia MRI scans. The moderate pain intensity value will be used for both pre- and post-rTMS analgesia MRI sessions.
- Hypnotic Induction Profile: This administration of the HIP will serve as the baseline measure for comparison after the rTMS stimulation session(87). HIP will be measured on three separate occasions throughout the stroop assessment visit - 1) immediately following the pre-rTMS analgesia MRI session, 2) immediately following rTMS, and, 3) immediately following the post-rTMS analgesia MRI session.
- Pre-TMS Scans
 - Structural Acquisition (T1): This structural scan is necessary for several reasons: demonstration that the participant's brain is structurally normal, imaging analysis, and rTMS targeting (81).
 - BOLD fMRI Acquisitions
 - Resting State: This is the baseline scan required for the primary endpoint. Individuals with higher hypnotizability have been demonstrated to have

higher functional connectivity between the dorsolateral prefrontal cortex and the dorsal anterior cingulate cortex (31).

- Pain Induction: Functional brain responses to acute, thermally, induced pain, will be measured using the moderate pain intensity value following hypnosis (Hypnotic Analgesia) and non-hypnosis (Non-Hypnotic Analgesia) audio instructions. These acquisitions will be randomized to prevent order effects. Hypnotic analgesia during pain induction has been demonstrated to be instruction specific (38, 44) and produce alterations in functional connectivity (123).

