6.2.5 Post-rTMS (Active and Sham) Evaluations

Post-rTMS Stroop Assessment

Hypnotic Stroop and Non-Hypnotic Stroop Pre-rTMS Scan Session: This session includes all of the post-rTMS behavioral evaluations and scans necessary to compare to the pre-rTMS.

- Hypnotic Induction Profile: This administration of the HIP will serve as the post-rTMS measure for comparison to the pre-rTMS stimulation session.
- Post-TMS Hypnotizability Scan Session (1 hour duration)
 - Structural Acquisition (T1): This structural scan is necessary for several reasons: demonstration that the participant's brain is structurally normal, imaging analysis, and rTMS targeting(81).
 - BOLD fMRI Acquisitions
 - Resting State: This is the scan required for evaluation of the primary endpoint. Individuals with high hypnotizability have been demonstrated to have higher functional connectivity between the dorsolateral prefrontal cortex and the dorsal anterior cingulate cortex (31).
 - Stroop Task: Brain activity while performing conflict tasks has been demonstrated to be different depending on a subject's level of hypnotizability. These scans will demonstrate the subject's functional brain response to the Stroop Task post-rTMS. Functional brain response to the stroop task will be measured following hypnosis (Hypnotic Stroop) and non-hypnosis (Non-Hypnotic Stroop) audio instructions. Randomization of hypnosis and non-hypnosis scan order for each participant will be kept consistent between both pre- and post-rTMS scans. Highly hypnotizable individuals can have a loss of the Stroop Effect with specific post-hypnoitic instruction (119, 120) which correlates with the reduction in neural activity

during conflict (35).

Post-rTMS Analgesia Assessment

Post-rTMS Analgesia Session: This hour-long scan session includes all of the post-rTMS behavioral evaluations and scans necessary to compare to the pre-rTMS.

- Hypnotic Induction Profile: This administration of the HIP will serve as the baseline measure for comparison after the rTMS stimulation session(87).
- Pre-TMS Scans
 - Structural Acquisition (T1): This structural scan is necessary for several reasons: demonstration that the participant's brain is structurally normal, imaging analysis, and rTMS targeting (81).
 - BOLD fMRI Acquisitions

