Connectivity between L-DLPFC and dACC will be assessed with resting state functional connectivity MRI(31, 51) at the baseline time-point and as well as at the post-rTMS time-point for both rTMS conditions (active and sham cTBS). Analyses will be restricted to the dACC and L-DLPFC for this Secondary Outcome Measure. To determine if rTMS condition during the hypnotic state is specifically associated with change in dACC and DLPFC activity and functional connectivity, a mask restricted to dACC and DLPFC will be utilized to extract the fMRI activity and connectivity data. It is expected that the correlation in active rTMS group over L-DLPFC to be stronger than the correlation obtained in the sham rTMS group. Regression analysis will determine the strength of the relationship between the reductions of fMRI activity between dACC and L-DLPFC during the active versus sham rTMS conditions. Regression analysis will be used to investigate whether greater connectivity will be present between L-DLPFC and dACC for active rTMS versus sham rTMS.

Secondary Outcome Measure B: *To determine the effect of active, inhibitory rTMS (cTBS) over L-DLPFC on enhancing hypnotizability (as measured by the Hypnotic Induction Profile-HIP and Stroop Task) and hypnotic intensity (as measured by the Hypnotic Intensity Scale-HIS).*

Augmenting hypnosis with active rTMS may potentially produce an intervention that works better (i.e. deeper hypnotic state) and/or extends to a larger part of the population (makes more of the population hypnotizable)(26).

Hypnosis Related Measures: All participants will receive a baseline Stroop task, HIP, and HIS. After randomization (to either active DLPFC rTMS or sham rTMS) where one half (n=45) will receive active rTMS (cTBS), and one-half sham rTMS (cTBS) (n=45)(30), participant will be placed back in scanner and their HIS will be reassessed. After the post-rTMS scans, all participants will be reassessed with the Stroop task and the HIP.

Analysis of Measures: Changes in HIP, Stroop Effect, and HIS between active DLPFC rTMS and sham rTMS conditions will be compared using ANOVA. It is expected that there will be a significantly greater mean increase in HIP, HIS, and Stroop Effect with active rTMS condition than with the sham rTMS condition at the $p < 0.05$, level.

Secondary Hypothesis B: *Active, inhibitory rTMS over DLPFC will increase hypnotizability and hypnotic intensity as compared to sham rTMS.*

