Hypnosis Scans for Secondary Outcome Measure D: All participants will receive the same identical pre-rTMS post-hypnotic suggestion Stroop task scan(35). After randomization (to either active DLPFC rTMS or sham rTMS) where one half (n=45) will receive active DLPFC rTMS (cTBS), and one-half sham DLPFC rTMS (cTBS) (n=45)(30), all participants have their post-rTMS post-hypnotic suggestion Stroop task scan session(35).

fMRI Preprocessing and Analysis: All fMRI data will be preprocessed and analyzed using FSL (FMRIB Software Library, version 5.0) and in the manner described in the Primary Outcome Measure. For group analysis, FMRIB's local analysis of mixed effects will be used within a mask of our a priori ROIs ACC and DLPFC, thresholded using family-wise error (FWE) corrected $Z > 2.3$; cluster $p < 0.05$. Average contrast of parameter estimate values will be extracted from the ROIs and Spearman's correlations will be calculated between these values and differences in active versus sham rTMS.

Secondary Hypothesis D: Post-hypnotic instruction of word blindness after active, inhibitory rTMS (cTBS) over L-DLPFC will reduce dACC activity during the Stroop task (similar to high hypnotizables) as compared to sham rTMS (sham cTBS).

Activity in dACC will be assessed with fMRI(35) at the baseline time-point and as well as at the post-rTMS time-point for both rTMS conditions (active and sham). Long-lasting (~1 hour) inhibitory rTMS (spaced continuous theta-burst stimulation approach(30)) will be applied to L-DLPFC and expect that the stimulation-induced functional connectivity between these two nodes would be increased as a surrogate of increased hypnotizability and therefore increased post-hypnotic Stroop Effect.

Analyses will be restricted to the dACC and DLPFC for this Secondary Outcome Measure. To determine if rTMS condition during the hypnotic state is specifically associated with change in dACC and DLPFC activity, a mask restricted to dACC and DLPFC will be utilized to extract the fMRI activity. The correlation in active rTMS group over L-DLPFC is expected to be stronger than the correlation obtained in the sham rTMS group. Regression analysis will determine the strength of the relationship between the reductions of fMRI activity between dACC and L-DLPFC with active versus sham rTMS conditions.

Secondary Outcome E: *To determine the effect of active, inhibitory rTMS over DLPFC on modulating the neural network that underlies hypnotic analgesia.*

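### The SAP tests the HIP change only at the immediate post-stimulation score, without a reason, although protocol section 9.6.2 reassesses HIP after the post-rTMS scans

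*SAP*

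**What the plan says.** **SAP.** The pre-to-post HIP changes "were calculated by subtracting the immediate post-spaced SHIFT score from the pre-spaced SHIFT score". I take SHIFT, which the SAP does not define, to be the spaced cTBS. Active and sham are compared on this change with a two-sided Mann-Whitney test. The SAP explains why ANOVA was replaced by non-parametric tests, but not why this post-stimulation score was used. It is in the past tense and reports Shapiro-Wilk results.

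**Protocol, section 9.6.2, Secondary Outcome Measure B.** The reassessment comes later: "After the post-rTMS scans, all participants will be reassessed with the Stroop task and the HIP". Change in HIP is then to be compared between the arms.

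**Protocol, section 6.2.2.** HIP is taken three times on each scan day. HIP 1 follows the pre-rTMS scan. The other two on the Stroop day are "2) immediately following rTMS, and, 3) immediately following the post-rTMS stroop MRI session", and on the analgesia day "2) immediately following rTMS, and, 3) immediately following the post-rTMS analgesia MRI session". I call these HIP 2 and HIP 3.

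**Protocol, section 6.2.5.** For the Stroop day, "This administration of the HIP will serve as the post-rTMS measure for comparison to the pre-rTMS stimulation session", without saying whether this is HIP 2 or HIP 3. For the analgesia day, the HIP listed among the post-rTMS evaluations is described as a baseline measure.

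**Duration of effect.** Section 3 says "this study will require more than an hour of modulation of the target in order to complete the scan sessions". Section 9.6.2, Secondary Hypothesis D, says "Long-lasting (~1 hour) inhibitory rTMS (spaced continuous theta-burst stimulation approach(30)) will be applied to L-DLPFC". Section 5.1 (Dosing Schedule) speaks of several hours of changed cortical excitability.

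**The concern.** HIP 2 and HIP 3 answer different questions. HIP 2 asks whether stimulation raises hypnotizability at once. HIP 3 asks whether it is still raised when the scan ends. The protocol's outcome section names the later score, and the SAP tests the earlier one. When two scores are scheduled and the choice between them appears, unexplained, in a document that already reports features of the data, a reader cannot tell whether it was fixed in advance.

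The design makes this more than a labelling matter. The spaced stimulation was chosen so that the effect would cover the post-rTMS scan, and the clinical hypothesis relies on raised hypnotizability during hypnotic analgesia. A difference at HIP 2 alone is likely to be reported simply as stimulation raising hypnotizability, with persistence assumed. Section 9.1 also plans to explore whether the effect on hypnotizability is mediated by the change in connectivity. The post-rTMS connectivity scan follows HIP 2, so with HIP 2 as the outcome, the outcome would be measured before the mediator.

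**Working it through.** **1. Scores available.** There are two scan days with two post-rTMS scores each, so 2 × 2 = 4 possible changes from the same-day HIP 1. The SAP uses HIP 2 and does not name the day.

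**2. Which score each text names.**

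| Place | Post-rTMS HIP |
|---|---|
| Protocol 6.2.2 | both HIP 2 and HIP 3 collected |
| Protocol 6.2.5 | one comparison measure, time point not stated |
| Protocol 9.6.2, Outcome B | after the scans, so HIP 3 |
| SAP | HIP 2 only |

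Listing order does not settle 6.2.5. HIP stands above the scan there, but section 6.2.2 also lists the baseline HIP above the pre-rTMS scan while stating that it is taken after that scan.

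**3. Gap between the scores.** Section 6.2.5 gives the post-rTMS Stroop-day scan as one hour and calls the analgesia session hour-long. HIP 3 therefore comes about 60 minutes or more after HIP 2. If HIP 2 takes 5 to 10 minutes and set-up 5 to 15 minutes (both my assumptions), HIP 3 falls between 5 + 5 + 60 = 70 and 10 + 15 + 60 = 85 minutes after stimulation.

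**4. Set against the duration statements.** The figure of more than an hour in section 3 is a requirement, not an estimate. The two estimates are about one hour (9.6.2, Hypothesis D) and several hours (5.1). On the first, HIP 3 lies near or beyond the stated duration; on the second, well within it. The documents do not settle persistence, and HIP 2 cannot.

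**5. How little one score says about the other (illustration only).** The documents give no effect size, SD or power for HIP. Their only power figure is for connectivity: 0.8 with 40 usable participants per arm and d = 0.8. With d taken as a standardized difference in change, the normal approximation gives Φ(0.8 × √(40/2) − 1.96) = Φ(1.618) = 0.947, so the stated 0.8 is not reproduced. That is a separate matter, and nothing here depends on it.

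Borrow d = 0.8 for HIP 2 as an assumption, with Mann-Whitney efficiency 0.955. The effective n per arm is 40 × 0.955 = 38.2. If a fraction f of the effect remains at HIP 3, power there is Φ(0.8 × f × √19.1 − 1.96), with √19.1 = 4.370:

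| f | 0.8 × f × 4.370 − 1.96 | Power at HIP 3 |
|---|---|---|
| 1.00 | 1.536 | 0.94 |
| 0.75 | 0.662 | 0.75 |
| 0.50 | −0.212 | 0.42 |
| 0.25 | −1.086 | 0.14 |

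A clear result at HIP 2 leaves HIP 3 open. Equally, a non-significant HIP 3 would not show that the effect had gone.

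**The case against.** The protocol does not fix one time point throughout. HIP 2 is a scheduled measure, section 6.2.5 leaves the comparator open, and the hypothesis text speaks only of pre- and post-rTMS scores. Section 9.6.2 may be older wording, since it gives 45 per arm where the précis gives 50; that is inference. The SAP refers to a preregistered plan, which may have named HIP 2. HIP is a secondary outcome, the P values are labelled nominal, and section 9.7 stresses effect size over significance for secondary aims. The SAP is one paragraph and also omits connectivity, pain, Stroop and the Hypnotic Intensity Scale (HIS), so HIP 3 is not singled out.

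Much of this stands. The SAP chose one of two legitimate scores, and HIP 3 remains scheduled. It does not explain the choice, and it does not remove the conflict with the only text that places the outcome reassessment in time.

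A reader might go further in four ways that the documents do not support:

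- **That HIP 3 is the only behavioural check on persistence.** Outcome B also uses the Stroop task, reassessed after the scans, and HIS, reassessed in the scanner.
- **That the choice of HIP 2 favours a positive finding.** No HIP 3 result is shown, so its direction is unknown.
- **That the effect has faded by HIP 3.** The one-hour figure is approximate, section 5.1 gives a longer one, and no decay curve is given.
- **That the scan objectives stand or fall with HIP 3.** They have their own sham-controlled comparisons. HIP 3 follows the scan, so a null there is compatible with an effect during it. Section 9.6.1 also assesses pain temperatures over only 30 minutes after rTMS and hypnotic analgesia.

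**Conclusion.** The point holds as a mismatch between documents and an unexplained choice of time point. Section 9.6.2 places the HIP reassessment after the post-rTMS scans; the SAP, which reports data already examined, tests only the immediate score and leaves the later one unanalysed. The scores are about 60 minutes or more apart on the documents' own scan length, and the design needs an effect of more than an hour. The SAP's HIP result can therefore support an immediate effect on hypnotizability, not a lasting one.

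The conclusion rests on the timing text and on reading SHIFT as the spaced cTBS. It does not rest on the 70 to 85 minute range or on the power illustration, both of which use assumptions. The consequence for the HIP estimate cannot be sized because no HIP effect is given. The primary connectivity outcome is unaffected. This should be corrected, but it does not invalidate the trial.

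**What to change.** In the SAP:

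- Report the active-versus-sham comparison of change from HIP 1 to HIP 3 beside HIP 1 to HIP 2 by the same method, or fit one arm-by-time model to both post-rTMS scores.
- Identify HIP 3 as the time point named in section 9.6.2, and state why HIP 2 was analysed and when that was decided, citing the preregistered plan if it says so.
- State which scan day is used, or how the two days are combined.
- Describe a result seen only at HIP 2 as an immediate effect on hypnotizability.

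In the protocol, reconcile the HIP timing in sections 6.2.5 and 9.6.2, and the after-effect duration in section 5.1 with that in 9.6.2, Hypothesis D.

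The protocol already schedules the data, so the cost is SAP wording and one more comparison. The downside is that the stated conclusion may become narrower.
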